2.1.1 General definitions

2.1.1.1 Treatment groups

In the final analysis, the summaries by treatment will be performed by the treatment sequence.

- Treatment sequence:

- AIN457 150 mg – AIN457 150 mg
- AIN457 150 mg – AIN457 [REDACTED]
- Placebo – AIN457 150 mg
- Placebo – AIN457 [REDACTED]

For some safety summaries (e.g., exposure-adjusted) the ‘switch’ treatment may be summarized separately:

- Entire study: Placebo, Any AIN457 150 mg, Any AIN457 [REDACTED], Any AIN457.

In the safety and efficacy listings, the groups will be presented by treatment sequence.

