2.1.1.2 Study Day 1 and other study days

The first day of administration of randomized study treatment (first dose) is defined as Study Day 1 or Day 1.

All other study days will be labeled relative to Day 1. For event dates on or after Day 1, study day for a particular event date is calculated as [Date of event] – [Date of first dose] + 1, i.e., Day 2, Day 3, etc., will be one day, two days, etc., after Day 1, respectively. For the dates before Day 1, study day for an event date is calculated as [Date of event] – [Date of first dose], i.e., Day -1, Day -2, etc., will be one day, two days, etc., before Day 1, respectively. Duration of an event will be calculated as (Event end date – Event start date + 1).

The descriptor “Day 0” will not be used.

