2.7 Safety analyses

Summaries will be performed for the entire treatment period on the Safety Set.

Safety analysis will be performed on treatment received or actual treatment as described below:

The actual treatment or treatment received for summaries of safety data would differ to the treatment assigned at randomization only if a subject received the wrong treatment during the entire study.

For those subjects who received not the treatment assigned at randomization, i.e., who received erroneously the wrong treatment at least once, an additional AE listing will be prepared displaying which events occurred after the treatment errors.

Subjects who switch treatment during the study (e.g. from placebo to active treatment) will be counted to both groups using the appropriate start and stop exposure date.

The safety variables to be analyzed include Adverse events (AEs)/Serious Adverse Events (SAEs), clinical laboratory tests (hematology, chemistry and urinalysis), physical examination results, ECGs, vital signs and deaths. Safety variables are to be tabulated by descriptive statistics (n, mean, median, standard deviation, minimum, and maximum; or n and percent). No formal statistical testing is planned.

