5.3.2 AE date imputation

Impute AE end date:

1. If the AE end date ‘month’ is missing, the imputed end date should be set to the earliest of the (min (last visit date, last dose data + 84 days), 31DECYYYY, date of death).
2. If the AE end date ‘day’ is missing, the imputed end date should be set to the earliest of the (min (last visit date, last dose data + 84 days), last day of the month, date of death)
3. If AE ‘year’ is missing or AE is ongoing, the end date will not be imputed.

Impute AE start date:

Before imputing AE start date, find the AE start reference date.

1. If the (imputed) AE end date is complete and the (imputed) AE end date < treatment start date then AE start reference date = min(informed consent date, earliest visit date).
2. Else AE start reference date = treatment start date
 1. If the AE start date ‘year’ value is missing, the date uncertainty is too high to impute a rational date. Therefore, if the AE year value is missing, the imputed AE start date is set to NULL.
 2. If the AE start date ‘year’ value is less than the treatment starts date year value, the AE started before treatment. Therefore:
 - a. If AE ‘month’ is missing, the imputed AE start date is set to the mid-year point (01JulYYYY).
 - b. Else if AE ‘month’ is not missing, the imputed AE start date is set to the mid-month point (15MONYYYY).
 3. If the AE start date year value is greater than the treatment starts date year value, the AE started after treatment. Therefore:
 - a. If the AE month is missing, the imputed AE start date is set to the year start point (01JanYYYY).
 - b. Else if the AE month is not missing, the imputed AE start date is set to the later of (month start point (01MONYYYY), AE start reference date + 1 day).
4. If the AE start date year value is equal to the treatment start date year value:
 - a. And the AE month are missing the imputed AE start date is set to the AE reference start date + 1 day.
 - b. Else if the AE month is less than the treatment start month, the imputed AE start date is set to the mid-month point (15MONYYYY).

- c. Else if the AE month is equal to the treatment start date month or greater than the treatment starts date month, the imputed AE start date is set to the later of (month start point (01MONYYYY), AE start reference date + 1 day).

If complete (imputed) AE end date is available and the imputed AE start date is greater than the (imputed) AE end date, then imputed AE start date should be set to the (imputed) AE end date.

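### Partial AE start dates are imputed with no branch for the Week 16 switch, so dates compatible with both periods fall to placebo in tables that split switchers by treatment

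*SAP*

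**What the plan says.** SAP 5.3.2 first fixes a reference date. If the AE ended before treatment started, it is the earlier of informed consent and the first visit. Otherwise: "Else AE start reference date = treatment start date". That section does not define treatment start date, but SAP 2.1.1.2 states: "The first day of administration of randomized study treatment (first dose) is defined as Study Day 1 or Day 1". For Group 2 that dose is placebo.

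The start-date rules that matter after first dose are:

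- Rule 4a, year of first dose, month missing: "And the AE month are missing the imputed AE start date is set to the AE reference start date + 1 day".
- Rules 3b and 4c, month known, day missing: "the imputed AE start date is set to the later of (month start point (01MONYYYY), AE start reference date + 1 day").
- Rule 3a, later year, month missing: "If the AE month is missing, the imputed AE start date is set to the year start point (01JanYYYY").
- Year missing: "if the AE year value is missing, the imputed AE start date is set to NULL".

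None refers to the Week 16 re-randomisation or to the first Treatment Period 2 dose.

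The imputed date then decides the column in some tables. Under SAP 2.7, participants who switch "will be counted to both groups using the appropriate start and stop exposure date". SAP 2.1.1.1 makes treatment sequence the grouping for the final analysis, but allows some safety summaries by actual treatment: "Entire study: Placebo, Any AIN457 150 mg", followed by a second, redacted secukinumab regimen and Any AIN457. SAP Table 2-1 plans exposure-adjusted incidence over the entire treatment period.

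**The concern.** Placing an ambiguous AE just after first dose is a cautious convention at the start of treatment, because it makes the event treatment-emergent. At Week 16 the same earliest-date convention works the other way for Group 2: it credits the ambiguous event to placebo and takes it from secukinumab. Any misplacement is therefore in one direction and favours the active drug.

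The SAP handles the switch elsewhere. Table 5-2 says which visit measurement to use when a participant moves from placebo to AIN457, and SAP 5.3.1 limits imputed study-drug dates to the end of the epoch. AE onset has no equivalent rule. With 20 participants planned per arm, one misplaced event is visible in a placebo column.

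**Working it through.** The plan gives no figure to reproduce. The check applies the SAP 5.3.2 rules to every possible date.

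**Inputs.** First dose is Day 1. The switch is on Day 113 (Week 16 target day, SAP Table 5-1). The treatment-emergent window ends at last dose + 84 days (SAP 2.7.1); with a Week 48 dose on Day 337, that is Day 421. Assumed: onset uniform over Days 2 to 421, AE end date missing or ongoing, all 365 first-dose dates of 2021 equally likely, and an onset on the switch day counted to placebo. A partial date is called ambiguous if it is compatible with onset both before and after the switch.

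**Worked dates.**

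- First dose 10 Nov 2021, switch 2 Mar 2022. Mar 2022 becomes 1 Mar 2022 (rule 3b) and year-only 2022 becomes 1 Jan 2022 (rule 3a). Both are placebo.
- First dose 10 Mar 2021, switch 30 Jun 2021. Year-only 2021 becomes 11 Mar 2021 (rule 4a), also placebo.

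**Enumeration.** Cases: 365 × 420 = 153,300. Post-switch onsets: 365 × 308 = 112,420.

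| | Day missing | Day and month missing |
|---|---|---|
| Ambiguous dates | 10,746 | 99,386 |
| Assigned to placebo | 10,746 | 99,386 |
| Of these, true onset after the switch | 5,373 (50.0%) | 64,834 (65.2%) |
| Share of all post-switch onsets credited to placebo | 5,373/112,420 = 4.8% | 64,834/112,420 = 57.7% |
| Pre-switch onsets credited to secukinumab | 0 | 0 |

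The percentages apply only to AEs whose dates are partial in that way. Counting the switch day as active gives 4.8% and 57.5% in the fourth row.

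**Scale of one event**, assuming 20 Group 2 participants with full follow-up:

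- Placebo exposure: 20 × 112/365.25 = 6.1 patient-years, so one event is 100/6.13 = 16.3 per 100 patient-years.
- Group 2 exposure after the switch: 20 × 308/365.25 = 16.9 patient-years, so one event is 100/16.87 = 5.9 per 100 patient-years.
- Any AIN457 also includes Group 1. With 20 more participants, 20 × 420/365.25 = 23.0 patient-years, and one event is 100/(16.87 + 23.00) = 2.5 per 100 patient-years.

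**Effect of a switch-aware rule.** Moving ambiguous dates to at least the day after the switch reduces post-switch onsets credited to placebo from 5,373 and 64,834 to 0 and 0. It credits 5,373 (50.0% of ambiguous) and 34,552 (34.8%) pre-switch onsets to secukinumab instead.

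**The case against.** Four objections deserve an answer.

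1. **The default tables are immune.** SAP 2.1.1.1 says final-analysis summaries will be by treatment sequence, where a placebo-to-secukinumab participant stays in one column whatever the imputed date. The split grouping is worded as optional, safety is descriptive, and the Day 1 to Week 16 data were already presented. This stands and limits the point. It does not remove it, because SAP 2.7 counts switchers in both groups by exposure dates, and the exposure-adjusted summaries are the example given for the split.

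2. **Few dates will be this incomplete.** AEs are sought at every visit (protocol 10.1.1), visits are at most four weeks apart through Week 52, and missing values are queried (protocol 11.2). This stands. A year-only onset date should be very rare.

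3. **The rule is often right.** A reader might infer that it gives the wrong group whenever it applies. The documents do not support that: ambiguous dates include AEs that did begin on placebo. Dates compatible with only one period are also placed correctly. For example, 112 of 365 first-dose dates (31%) put the switch in the next calendar year; for those participants a post-dose AE dated only to the first-dose year did begin on placebo. Nor is the reference date always the first dose, since AEs that ended before treatment use consent or the first visit.

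4. **Another document may deal with it.** SAP 2.7.1 says date-imputation algorithms will be in the Programming Datasets Specifications, which cannot be seen here. A period-specific rule there is possible, but SAP 5.3.2 states a rule of its own without one, and the two would then have to agree.

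**Conclusion.** The point holds in a narrow form. For Group 2 participants who switch, SAP 5.3.2 sends an AE start date compatible with both periods to placebo, with at most one exception: when the switch falls on the imputed date itself. Under uniform onset, about half of such dates are misplaced when the day is missing and about two thirds when day and month are missing, always in favour of secukinumab. The effect is confined to summaries that split switchers by treatment.

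A reader might infer that the trial's AE tables in general understate secukinumab risk. The documents do not support that. The sequence tables are unaffected, the frequency of partial dates is not given, and the number of affected events is probably very small. This is a cheap improvement to one rule and does not threaten the safety conclusions. It rests on reading treatment start date as first dose, and on no overriding rule in the Programming Datasets Specifications.

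**What to change.** Add to SAP 5.3.2, for the summaries that split switchers by treatment only:

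For Group 2 participants who received a Treatment Period 2 dose, if the partial AE start date is compatible with onset on or after the first such dose, and the (imputed) AE end date does not precede that dose, the imputed start date is the later of the date given by rule 3a, 3b, 4a or 4c and the first Treatment Period 2 dose date + 1 day. The existing cap at the AE end date still applies.

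The sentence acts on the imputed date because changing only the reference date would miss rule 3a, which does not use it. Group 1 is left out: both its periods are active treatment, so its dates do not affect Placebo versus Any AIN457. When the dose falls on the last day of the recorded month, adding a day moves the date into the next month, as the existing rule already does at first dose.

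The cost is one sentence, a small derivation change, and the same wording in the Programming Datasets Specifications. The downside is that the error is moved rather than removed: some AEs that truly began on placebo will count to secukinumab. That is the conservative direction and matches how the SAP already treats ambiguity at first dose.

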5.3.3 Concomitant medication date imputation

Impute CM end date:

1. If CM end day is missing and CM month/year are non-missing, then impute CM day as the minimum of treatment end date and the last day of the month.
2. If CM end day/month are missing and CM year is non-missing, then impute CM day as the minimum of treatment end date and the end of the year (31DECYYYY).
3. If imputed CM end date is less than the CM start date, use the CM start date as the imputed CM end date.

Impute CM start date:

1. If the CM start date year value is missing, the imputed CM start date is set to one day prior to treatment start date.
2. If the CM start date year value is less than the treatment starts date year value, the CM started before treatment. Therefore:
 - a. If the CM month is missing, the imputed CM start date is set to the mid-year point (01JULYYYY)
 - b. Else if the CM month is not missing, the imputed CM start date is set to the mid-month point (15MONYYYY)
3. If the CM start date year value is greater than the treatment starts date year value, the CM started after treatment. Therefore:
 - a. If the CM month is missing, the imputed CM start date is set to the year start point (01JANYYYY)
 - b. Else if the CM month is not missing, the imputed CM date is set to the month start point (01MONYYYY)
4. If the CM start date year value is equal to the treatment start date year value:
 - a. And the CM month is missing, or the CM month is equal to the treatment start date month, then the imputed CM start date is set to one day prior treatment start date
 - b. Else if the CM month is less than the treatment starts date month, the imputed CM start date is set to the mid-month point (15MONYYYY)
 - c. Else if the CM month is greater than the treatment starts date month, the imputed CM start date is set to the month start point (01MONYYYY)

If complete (imputed) CM end date is available and the imputed CM start date is greater than the (imputed) CM end date, then imputed CM start date should be set to the (imputed) CM end date.

5.3.3.1 Prior therapies date imputation

See Section 5.3.2.

[figure not shown]
5.3.3.2 Post therapies date imputation

[figure not shown]
See Section 5.3.3.

